16.1 Study Information

16.1.1 Protocol and protocol amendments

The following document is included:

- [Final protocol, dated 06 Oct 2015](#)

CLINICAL STUDY PROTOCOL

Protocol No. TEN-01-302

A 26-Week, Randomized, Double-Blind, Placebo-Controlled Study to Evaluate the Efficacy and Safety of Tenapanor for the Treatment of Constipation-Predominant Irritable Bowel Syndrome (IBS-C)

6 October 2015
Edition No. 1

SPONSOR:

Ardelyx, Inc.
[name]
[name]

Confidentiality Statement

This document and the information contained herein or attached hereto ("Confidential Material") are confidential and proprietary to Ardelyx, Inc. This Confidential Material should be viewed only by those individuals or companies that have been given prior authorization to do so by Ardelyx, Inc. ("Authorized Users"). This Confidential Material should not be made available in any form to any person or company, other than the Authorized Users and their respective employees or associates on a need-to-know basis, without the prior written consent from Ardelyx, Inc.

PROTOCOL SUMMARY

Study Title	A 26-Week, Randomized, Double-Blind, Placebo-Controlled Study to Evaluate the Efficacy and Safety of Tenapanor for the Treatment of Constipation-Predominant Irritable Bowel Syndrome (IBS-C)
Sponsor	Ardelyx, Inc.
Study Phase	3
Treatment Groups	2 treatment groups; ~600 subjects total; ~300/group with a ratio of 1:1 Tenapanor:placebo
No. of Sites	100-120
Dose Form and Frequency	Tablet(s), placebo matched Twice daily (BID)
Doses	Placebo, and tenapanor 50 mg BID (total daily doses; placebo, and 100 mg)
Methodology	This is a 26-week, multi-center, randomized, double-blind, placebo controlled study to evaluate tenapanor 50 mg BID in subjects with IBS-C (Rome III criteria). A 2:1 screen to randomization ratio is expected.
Duration	For each subject, the entire study will last for a total of 28 weeks; including 26 weeks of treatment, preceded by a 2 week screening period.
2-Week Screening Period	
At the beginning of the 2-week screening period (Day -14), the following will be performed:
 
Subjects will provide written consent and be fully assessed for eligibility into the study. The assessments will include: inclusion/exclusion criteria, medical histories (including details about co-morbid disorders), physical exam, vital signs, ECG, and clinical laboratory tests. During the 2-week screening period, subjects will self-report, on a daily basis, information about the status of their IBS-C symptoms via an electronic diary.
 
At the end of the screening period, prior to the subject returning for Visit 2 (randomization), a member of the site staff will confirm a subject's eligibility with regard to the information they have reported in their electronic diary during screening. If the information captured in the diary deems them eligible, and they continue to meet the inclusion criteria, which includes meeting the Rome III criteria for IBS with constipation, then the subject will be randomized into a treatment group.

26-Week Treatment Period
	
During the 26-week double-blind treatment period, subjects will record daily assessments including: frequency and timing of bowel movements; sensation of complete bowel emptying; consistency of bowel movements (BSFS); degree of straining, worst abdominal pain, abdominal discomfort, abdominal bloating, abdominal fullness and abdominal cramping; and use and timing of rescue medication. Subjects will also record weekly assessments including: adequate relief of IBS symptoms, degree of relief of IBS symptoms, IBS severity, and constipation severity. The IBS-QOL questionnaire will be administered during screening, Week 12, and at the end of the study; and Treatment Satisfaction will be evaluated monthly. The subject will return for study visits every two, four or six weeks (see schedule of events). Subjects will undergo safety assessments at these visits, which may include a physical exam, ECG, vital signs, and clinical labs. Adverse events and concomitant medications will be recorded. Medication compliance will be monitored and the subjects will be given additional study drug as appropriate.


Inclusion/Exclusion Criteria
	
Inclusion Criteria
 
Subjects meeting all of the following inclusion criteria will be eligible for enrollment:
 
 1. 18 to 75 years old 2. Females must be of non-childbearing potential; either postmenopausal for at least 12 months as confirmed by follicle-stimulating hormone test (if < 60 years old), or surgically sterile (e.g., tubal ligation, hysterectomy, bilateral oophorectomy with appropriate documentation). If of child-bearing potential, must have negative pregnancy test at Visits 1 and 2, and confirm the use of one of the following appropriate means of contraception: 
 • oral birth control pills administered for at least one monthly cycle prior to study drug administration, • contraceptive patch worn for at least one monthly cycle prior to study drug administration, • progesterone implants, • IUDs, • abstinence from intercourse for two weeks prior to the study drug administration, throughout the 26-week treatment phase, or • double barrier method,

	
• sterilization of one or both partner(s). 
3. Males must agree to use an appropriate method of barrier contraception (e.g., latex condom with a spermicidal agent) or have documented surgical sterilization4. Subject is ambulatory5. Subject meets definition of IBS-C using Rome III Criteria (see Appendix A) for the Diagnosis of IBS6. Subject meets screening eligibility criteria7. Colonoscopy requirements
• Subjects, age 50 years or older, must have had a colonoscopy within 10 years of enrollment (American Gastroenterological Association guidelines).• Patients of any age with unexplained warning symptoms (e.g., lower gastrointestinal bleeding, iron-deficiency anemia, clinically significant weight loss, systemic signs of infection or colitis) must have had a colonoscopy, with non-significant findings, after the onset or worsening of the warning symptoms.8. Ability to communicate well with the Investigator and to comply with the requirements of the entire study, including an understanding of how to use the touch-tone telephone electronic diary9. Written informed consent and a willingness to participate in the study as it is described10. Daily access to a touch tone telephone 
Exclusion Criteria
 
Subjects meeting one or more of the following exclusion criteria are not to be enrolled in the study:
 
1. Functional diarrhea as defined by Rome III criteria (see Appendix A)2. IBS with diarrhea (IBS-D), mixed IBS (IBS-M), or unsubtype IBS as defined by Rome III criteria (see Appendix A)3. Pregnant or lactating women.4. Diagnosis or treatment of any clinically symptomatic biochemical or structural abnormality of the GI tract within 6 months prior to screening, or active disease within 6 months prior to screening; including but not limited to cancer, inflammatory bowel disease, diverticulitis, duodenal ulcer, erosive esophagitis, gastric
--	---

	
ulcer, pancreatitis (within 12 months of screening), cholelithiasis, amyloidosis, ileus, non-controlled GERD, gastrointestinal obstruction or carcinoid syndrome.
 
5. Subject has a potential CNS cause of constipation (e.g., Parkinson's disease, spinal cord injury, or multiple sclerosis)6. Use of medications that are known to affect stool consistency as described in Section 5.6 (Prohibited Medications). Note: Patients on a stable, continuous regimen of fiber, bulk laxatives, stool softeners, or probiotics during the 30 days before the screening visit are allowed to continue, provided they maintain a stable dosage throughout the trial.7. Clinical evidence of significant cardiovascular, respiratory, renal, hepatic, gastrointestinal, hematologic, neurologic, psychiatric or any disease that may interfere with the subject successfully completing the trial8. The subject has a history or current evidence of laxative abuse (in the clinical judgment of the physician)9. Hepatic dysfunction (ALT [SGPT] or AST [SGOT] >2.5 times the upper limit of normal) or renal impairment (serum creatinine > 2mg/dL)10. Any evidence of or treatment of malignancy (other than localized basal cell, squamous cell skin cancer or cancer in situ that has been resected) within the previous year11. Any surgery on the stomach, small intestine or colon, excluding appendectomy and cholecystectomy (unless within 60 days of screening visit)12. If, in the opinion of the Investigator the subject is unable or unwilling to fulfill the requirements of the protocol or has a condition, which would render the results uninterpretable13. A major psychiatric disorder (DSM-III-R or DSM-IV) including major depression or other psychoses that has required hospitalization in the last 3 years. History of attempted suicide or uncontrolled bipolar disorder.14. Alcohol or substance abuse in the last year15. Subject is involved in the conduct and/or administration of this trial as an investigator, sub-investigator, trial coordinator, or other staff member, or the subject was a first degree family member, significant other, or relative
--	--

	
residing with one of the above persons involved in the trial
 
16. Participation in other clinical trials within 1 month prior to Day -14 (beginning of screening period)
 
17. Subject has been randomized into any Phase 1 or 2 study in which tenapanor was a treatment

--	---


Screening Eligibility Criteria to qualify for the Treatment Period
	
Subject eligibility, according to the IBS symptom information captured in the diary during the 2-week screening period, will be determined electronically by the interactive voice-response system and provided to the clinical staff via IWRS.
 
 • Subjects must have $\geq 78\%$ compliance (≥ 11 of 14 days) with completing the daily assessments via the touch-tone telephone diary • Subjects must have a weekly stool frequency of < 3 CSBMs (complete spontaneous bowel movements) and ≤ 5 SBMs (spontaneous bowel movements) • Subjects must have a mean stool consistency score of ≤ 3 using the 7-point Bristol Stool Form Scale (BSFS) (see Appendix B) • For the daily assessment of abdominal pain, subjects must have an average weekly abdominal pain score of ≥ 3 on a 0-10 point scale. • Rescue medication as defined in Section 5.5, usage for ≤ 2 of the 14 days; none within 48 hours prior to randomization • No use of a prohibited medication, except rescue medication as defined in Section 5.5 • No watery stools (Type 7 on the Bristol Stool Form Scale; (see Appendix B) for any SBM, or loose (mushy) stools (Type 6 on the BSFS) for > 1 SBM

Efficacy Variables:
	
Primary:
 
 • 6/12 week overall responder rate (weekly responder for the first 6/12 weeks for both CSBM and abdominal pain, described below) vs placebo 
Key Secondary:
 
 • 6/12 week overall CSBM responder rate (weekly responder for the first 6/12 weeks; ≥ 1 CSBM from baseline) vs placebo • 6/12 week overall abdominal pain responder rate (weekly responder for the first 6/12 weeks; decrease of $\geq 30\%$ of worst abdominal pain from baseline) vs placebo • 13/26 week overall responder rate (weekly responder for 13/26 weeks for both CSBM and abdominal pain) vs placebo • 13/26 week overall CSBM responder rate (weekly responder for 13/26 weeks; ≥ 1 CSBM from baseline) vs placebo • 13/26 week overall abdominal pain responder rate (weekly responder for 13/26 weeks; decrease of $\geq 30\%$ of worst abdominal pain from baseline) vs placebo

	
• 9/12 week overall responder rate (weekly responder for the first 9/12 weeks for both CSBM and abdominal pain, described below) vs placebo• 9/12 week overall CSBM responder rate (weekly responder for the first 9/12 weeks; ≥ 1 CSBM from baseline and ≥ 3 CSBM) vs placebo• 9/12 week overall abdominal pain responder rate (weekly responder for the first 9/12 weeks; decrease of $\geq 30\%$ of worst abdominal pain from baseline) vs placebo• Durable overall responder rate (weekly responder for the first 9/12 weeks and 3 of the last 4 weeks for both CSBM and abdominal pain, described below) vs placebo• Durable overall CSBM responder rate (weekly responder for the first 9/12 weeks and 3 of the last 4 weeks; ≥ 1 CSBM from baseline and ≥ 3 CSBM) vs placebo• Durable overall abdominal pain responder rate (weekly responder for the first 9/12 weeks and 3 of the last 4 weeks; decrease of $\geq 30\%$ of worst abdominal pain from baseline) vs placebo 
Other Secondary Variables
 
• Daily/weekly assessments of other bowel habits including: frequency of CSBMs, frequency of spontaneous bowel movements (SBMs), stool consistency, degree of straining, worst abdominal pain, abdominal discomfort, abdominal bloating, abdominal fullness, and abdominal cramping, IBS severity, constipation severity, IBS-QOL, adequate relief of IBS symptoms, degree of relief of IBS symptoms, and treatment satisfaction.
--	---


Statistical Considerations
	
Summary tabulations will be presented that will display descriptive statistics for each treatment group. For subject disposition, demographic and baseline characteristics, medical history, gastrointestinal disease history, and prior medications, an overall column (i.e., all subjects combined) will be included. For continuous variables, descriptive statistics will include the number of subjects, mean, standard deviation, minimum, median, and maximum values. For categorical variables, descriptive statistics will include the number and percent of subjects in each category.
 
All subjects who meet the study entry inclusion/exclusion criteria, receive at least one dose of study drug, and have at least one valid week of efficacy assessment data (minimum of 4 days) will be included in the ITT analysis set. Subjects will be analyzed according to the treatment group into which they were randomized. The ITT analysis set will be the primary analysis set for efficacy analysis.
 
Responder rate efficacy variables will be analyzed using a Cochran-Mantel-Haenszel (CMH) test with pooled investigator site as a stratification (adjustment) variable. Summary statistics will include the pairwise risk difference with placebo along with the asymptotic 95% confidence interval (CI). The adjusted relative risk (adjusted for pooled investigator site) will be based on the ratio of responder rates for placebo versus tenapanor. The 95% CI versus placebo will also be presented for the adjusted relative risk. Continuous efficacy variables will be analyzed using an analysis of covariance (ANCOVA) or analysis of variance (ANOVA) model. The ANCOVA model will have terms for pooled investigator site, treatment group, and baseline as the covariate. The ANOVA model will have terms for pooled investigator site and treatment group. The hypotheses will be based on the LS means difference from placebo.
 
Safety analyses will include summaries for adverse events, clinical laboratory tests, vital signs, 12-lead ECGs, and physical exams. Compliance and concomitant medications will also be summarized.

-----------------------------------	---

TABLE OF CONTENTS

PROTOCOL SUMMARY.....	2
TABLE OF CONTENTS.....	10
1. LIST OF ABBREVIATIONS.....	12
2. INTRODUCTION AND STUDY RATIONALE	15
2.1. Scientific Background	15
2.2. Description of Investigational Drug	15
2.3. Previous Human Experience	16
2.4. Dose Rationale.....	19
3. STUDY OBJECTIVES.....	20

1. LIST OF ABBREVIATIONS

AE	Adverse event
ALT	Alanine aminotransaminase
ANCOVA	Analysis of covariance
ANOVA	Analysis of variance
AST	Aspartate aminotransaminase
BM	Bowel movement
BMI	Body mass index
BQL	Below quantitation limit
BSFS	Bristol stool form scale
BUN	Blood urea nitrogen
CIC	Chronic idiopathic constipation
CKD	Chronic kidney disease
CMH	Cochran-mantel-haenszel
CO ₂	Carbon dioxide
CRA	Clinical research associate
CRC	Child resistant closure
CRF	Case report form;
CRO	Contract research organization
CSBM	Complete spontaneous bowel movement
CTCAE	Common terminology criteria for adverse events
DSM	Diagnostic and statistical manual of mental disorders
ECG	Electrocardiogram
eCRF	Electronic case report form
EDC	Electronic data capture
ESRD	End-stage renal disease
FDA	Food and drug administration
FSH	Follicle-stimulating hormone
GCP	Good clinical practice
GERD	Gastroesophageal reflux disease
GI	Gastrointestinal
H+	Hydrogen
HDPE	High density polyethylene
HEK	Human embryonic kidney cells

hERG	Human ether-a-go-go related gene
HPMC	Hydroxypropylmethylcellulose
IB	Investigator's brochure
IBS	Irritable bowel syndrome
IBS-C	Constipation predominant irritable bowel syndrome
IBS-D	Diarrhea predominant irritable bowel syndrome
IBS-M	Mixed irritable bowel syndrome (constipation and diarrhea)
IBS-QOL	Irritable bowel syndrome quality of life questionnaire
ICF	Informed consent form
ICH	International conference on harmonization
IEC	Independent ethics committee
IKr	Current amplitude
IRB	Institutional review board
ITT	Intent to treat
IVRS	Interactive voice response system
IWRS	Interactive web response system
LDH	Lactate dehydrogenase
LOCF	Last observation carried forward
LS	Least squares
MAD	Multiple ascending dose
MCH	Mean corpuscular hemoglobin
MCHC	Mean corpuscular hemoglobin concentration
MCV	Mean corpuscular volume
MedDRA	Medical Dictionary for Drug Regulatory Activities
Na ⁺	Water/sodium
NHE ₃	Sodium-hydrogen antiporter 3
NOAEL	No observed adverse effect level
NRS	Numeric rating scale
NSAID	Non-steroidal anti-inflammatory drug
OBD	Opioid bowel dysfunction
OC	Observed case
P	Probability; p-value
PD	Pharmacodynamic
PK	Pharmacokinetic

PRO	Patient reported outcome
QA	Quality assurance
QD	Once daily
RBC	Red blood cell
SAD	Single ascending dose
SAE	Serious adverse event
SAP	Statistical analysis plan
SBM	Spontaneous bowel movement
SGOT	Serum glutamic-oxaloacetic transaminase
SGPT	Serum glutamic-pyruvic transaminase
SOP	Standard operating procedure
TEAE	Treatment emergent adverse event
TLF	Tables, listings, and figures
WBC	White blood cell count
WHO	World health organization
WHODRL	World health organization drug reference library

2. INTRODUCTION AND STUDY RATIONALE

A major function of the gastrointestinal (GI) tract is to maintain intestinal water/sodium (Na⁺) homeostasis through a delicate balance of secretory and absorption mechanisms. The Na⁺/hydrogen (H⁺) antiporter NHE3 plays a dominant role in the Na⁺ re-uptake process. Tenapanor (also known as RDX5791 and AZD1722) is a GI-acting NHE3 inhibitor. Tenapanor is a minimally systemic, small molecule under investigation for the treatment of constipation-related diseases such as chronic idiopathic constipation (CIC), constipation predominant irritable bowel syndrome (IBS-C), and opioid bowel dysfunction (OBD). The proposed mechanism of action of tenapanor is to reduce Na⁺ re-uptake. This decrease in Na⁺ uptake increases the net fluid volume in the GI tract. Restoration of normal luminal fluid content facilitates intestinal transit and stimulates motility.

This phase 3, multi-center, randomized, double blind, placebo-controlled, multi-center study will evaluate the safety and efficacy of tenapanor in subjects with constipation predominant IBS (IBS-C) as defined by the Rome III criteria and who have active disease as determined during a two-week screening period. Subjects who qualify and are randomized into the study will receive tenapanor 50 mg BID or matching placebo BID for 26 consecutive weeks.

2.1. Scientific Background

2.1.1 Overview of IBS

Irritable bowel syndrome (IBS) is the most common disorder seen by gastroenterologists and is characterized by abdominal pain with associated alterations in bowel function. These changes in bowel patterns may manifest as diarrhea, constipation or an alternation between the two. As there are no pathognomonic, laboratory, endoscopic or radiographic abnormalities found in association with IBS it is considered a functional gastrointestinal (GI) disorder. The chronic nature of the multiple symptoms of IBS, combined with the lack of effective treatments, leads to significant health care resources being used by IBS subjects and impairment of subjects' well-being and functional ability. For research and regulatory purposes, the diagnosis of IBS has been described by the Rome III criteria as summarized in [Section 14 \(Appendix A\)](#).

2.2. Description of Investigational Drug

Tenapanor is chemically described as: (S)-N,N'-(10,17-dioxo-3,6,21,24-tetraoxa-9,11,16,18-tetraazahexacosane-1,26-diyl)bis(3-((S)-6,8-dichloro-2-methyl-1,2,3,4-tetrahydroisoquinolin-4-yl) benzenesulfonamide) dihydrochloride. Its empirical formula is C₅₀H₆₈C₁₆N₈O₁₀S₂.

Tenapanor (as the dihydrochloride salt) drug product will be supplied as white to off-white oval biconvex film-coated tablets with the following excipients: [REDACTED]

[REDACTED] Tenapanor will be supplied at a dosage strength of 50 mg. Tablets are packaged in an opaque white HDPE (high-density polyethylene) bottle (66/bottle) with a white polypropylene CRC closure and induction seal plus

desiccants. Tablets of tenapanor should be stored in the original packaging between 2°C and 30°C. Temperature excursions are allowed from -30°C to 50°C excursions for a maximum of 1 week.

2.3. Previous Human Experience

2.3.1 Safety

[REDACTED]

[REDACTED]

[REDACTED]

2.3.2 Efficacy

[REDACTED]

[REDACTED]

2.4. Dose Rationale

Results from the Phase 2b study in IBS-C demonstrated that tenapanor 50 mg BID had statistically significant effects in the primary endpoint of CSBM responder rate with consistent effects in both overall and abdominal pain responder rates. Results from this study also demonstrated that 20 mg BID (the next lowest dose) did not have statistically significant effects in key endpoints. Based on results from this double-blind, placebo-controlled study, 50 mg BID was selected as the dose for this pivotal phase 3 clinical trial.

3. STUDY OBJECTIVES

3.1. Primary Objective

The primary objective of this study is:

To assess the efficacy of tenapanor 50 mg for the treatment of IBS-C when administered twice daily (BID) for 26 consecutive weeks.

3.2. Secondary Objectives

The secondary objective of this study is:

To assess the safety and tolerability of tenapanor 50 mg when administered twice daily (BID) for 26 consecutive weeks.

3.3. Exploratory Objective

The exploratory objective of this study is:

To collect and store DNA for future exploratory research into serum biomarkers and genes/genetic variation related to the gastrointestinal disease area or that may influence response (i.e., distribution, safety, tolerability and efficacy) to tenapanor.

4. INVESTIGATIONAL PLAN

This is a Phase 3, multi-center, randomized, double-blind, placebo controlled study of tenapanor in subjects with IBS-C. Patients who are 18 to 75 years old, meeting the definition of IBS-C as defined by the Rome III Criteria for the Diagnosis of IBS (see [Appendix A](#)) will undergo a battery of screening procedures to determine eligibility for the trial. A 2:1 screen to randomization ratio is expected.

The study will consist of a 2-week screening period, and a 26-week treatment period.

Two weeks prior to study randomization, prospective subjects may be assessed with respect to their meeting the eligibility requirements of the study.

At the beginning of the 2-week screening period (Day -14), subjects will be questioned with respect to their eligibility for the study. Those that meet the basic requirements will be asked to provide written informed consent. The basic screening assessments will include: evaluation of the inclusion/exclusion criteria, medical history (including details about co-morbid disorders), physical exam, vital signs, ECG, and clinical laboratory tests, including urinalysis. Subjects must discontinue the use of all prohibited medications at Visit 1 (Screening/Day -14) for the duration of the study, as referenced in [Section 5.6](#). During the screening period, and starting on the evening of Study Visit 1, subjects will self-report daily information about the status of their IBS symptoms via a touch-tone telephone diary. Each day, entries into the telephone diary (IVRS diary) must occur between 6PM and 11:59PM (local time). This will include information about their stool frequency, stool consistency, straining, abdominal pain, abdominal discomfort, abdominal bloating, abdominal fullness, abdominal cramping, and rescue medication usage. Additionally, on a weekly basis, the IBS severity and constipation severity will also be collected through the IVRS diary. Subject compliance with the electronic diary will be monitored actively by the site staff and by the electronic diary system.

At the end of the screening period, prior to the subject returning for Visit 2 (Randomization), a member of the site staff will confirm a subject's eligibility with regard to the information they have reported in their electronic diary during screening. If the information captured in the diary deems them eligible, and they continue to meet the inclusion criteria at Visit 2, a member of the site staff will randomize the subject into a treatment group using an interactive web-response system (IWRS).

Subjects will be randomized into a treatment group according to a computer-generated central randomization schema. All subjects who receive at least one dose of study drug, with at least one valid week of efficacy assessment data will be included in the intention-to-treat (ITT) analysis set. All subjects who receive at least one dose of study drug will be included in all analyses of safety data.

During the 26-week double-blind treatment period, subjects will continue to record daily and weekly assessments via a touch-tone telephone diary system as instructed. Subjects will be seen weeks 2, 4, 8, 12, 16, 20, and 26 (Days 15, 29, 57, 85, 113, 141, and 183) during the treatment period. Subject compliance with daily diary entries will be monitored on an ongoing basis by the clinical site staff. Subject compliance

with study drug will also be monitored closely by clinical site staff throughout the study

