5.6. Prohibited Concurrent Medications

Administration of any concomitant therapy during the 7 days prior to the screening period, during the screening, and treatment periods should be recorded on the appropriate CRF page. The following medications are specifically prohibited from use during the study (including screening period), unless specified as a rescue medication and used according to the procedure outlined in Section 5.5.

- Antidiarrheals
- Antacids which contain aluminum and/or magnesium (if used more than 3 days per week)
- Enemas (except as defined in Section 5.5)
- Antinausea agents (e.g., benzquinamide, trimethobenzamide)
- Antispasmodic agents (e.g., Donnatal®, Librax®)
- Laxatives or stool softeners (except a stable dose as defined in [Section 5.3, #4](#))
- Prokinetic agents (e.g., cisapride, metoclopramide)
- Macrolide antibiotics (e.g., erythromycin, azithromycin)
- Cholestyramine or WelChol®
- 5-HT₃ antagonists (e.g., alosetron, ondanestron)
- 5-HT₄ agonists (e.g., tegaserod)
- Bismuth preparations
- Anticholinergics (e.g., dicyclomine)
- Narcotics and narcotic containing analgesics, including tramadol
- Iron supplements (with the exception of multivitamins containing Iron and those individuals on a stable dose for > 30-days prior to screening period of Iron supplements)
- NSAIDS (if used more than 3 days per week); Aspirin ≤ 325 mg per day is allowed
- All other analgesics (if used more than 3 days per week)
- Anti-Parkinson agents (e.g. levodopa, deprenyl)
- Antipsychotics, allowed if on a stable dose for > 30-days prior to screening period
- Anticonvulsants used for seizure disorders
- Antidepressants, allowed, if on a stable dose for > 30-day prior to screening period
- Stimulants and amphetamine-like drugs

- Misoprostol, alone or in combination
- Lubiprostone (Amitiza[®]) or Linaclotide (Linzess[®])

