7. SCHEDULE OF ASSESSMENTS

The study flow chart, including all procedures to be performed during the study is presented below. Prior to engaging in any study procedure, each subject must sign and date an informed consent form.

Evaluation	Screen	Treatment Period							
		1	2	3	4	5	6	7	8
Site Visit	-2	0	2	4	8	12	16	20	26
Study Week	-14	1	15±3	29±3	57±3	85±3	113±3	141±3	183±3
Study Day(s)									
Informed Consent ^a	X								
Inclusion/Exclusion	X	X							
Demographics	X								
Medical History (including GI history)	X	X ^b							
Prior/Concurrent Medications	X	X	X	X	X	X	X	X	X
Physical Exam	X								X
Vital Signs ^c	X	X	X	X	X	X	X	X	X
Height	X								
Serum Chemistry and Hematology	X			X		X			X
Pharmacogenomics sample ^e				X		X			X
Biomarker sample	X			X		X			X
FSH test ^d	X								
Serology	X								
Urine Pregnancy test ^d	X	X		X		X			X
Urinalysis	X			X		X			X
12-lead electronic ECG	X					X			X
IVRS Training/Compliance Check & Reminder	X	X	X	X	X	X	X	X	

Evaluation	Screen	Treatment Period							
		2	3	4	5	6	7	8	9/ET ^f
Site Visit	1								
Study Week	-2	0	2	4	8	12	16	20	26
Study Day(s)	-14	1	15±3	29±3	57±3	85±3	113±3	141±3	183±3
IBS-QOL PRO		X				X			X
Treatment Satisfaction PRO				X	X	X	X	X	X
Randomization		X							
Daily PROs ^e	X	X	X	X	X	X	X	X	X
Drug Dispensed/returned		D		D/R	D/R	D/R	D/R	D ^h /R	R
Adverse Event Assessments			X	X	X	X	X	X	X

^aThe Informed Consent Form (ICF) must be signed before any study procedures are performed and prior to discontinuing any prohibited medications; The ICF may be signed before the Screening Visit.

^bMedical history for Visit 2; record only changes to Medical history from Visit 1.

^cVital signs include systolic and diastolic blood pressure (seated), heart rate, respiratory rate, temperature and body weight.

^dFSH is performed in post-menopausal women (at screening only); pregnancy tests are performed on all females <60 years of age unless there is a documented method of sterilization, or FSH test confirms post-menopausal status

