8.1.1 Evaluations and procedures at Visit 1 (Day -14)

The procedures outlined for Visit 1 must be completed prior to enrolling the subject into the study. The following procedures will be conducted at Visit 1:

- Informed Consent (must be signed prior to discontinuing any prohibited medications or prior to the conduct of any study-related procedure)
- Inclusion/Exclusion Criteria
- Demographics
- Medical History, including IBS-C and other GI history
- Prior and Concurrent Medications
- Physical Exam
- Vital Signs
- Height
- Serum Chemistry and Hematology
- Biomarker sample
- FSH Test, as appropriate
- Serology
- Urine Pregnancy Test
- Urinalysis
- ECG
- Subjects will be instructed on the use of the telephone diary and begin

calling into the diary the evening of Visit 1 (Day -14)

- Subjects will be instructed to discontinue the use of all prohibited medications as outlined in [Section 5.6](#).

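### The Visit 1 instruction to stop all prohibited drugs covers seizure anticonvulsants, and nothing clearly excludes a well-controlled seizure patient or says the drug must not be stopped to qualify

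*Protocol*

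**What the plan says.** Protocol Section 4: "Subjects must discontinue the use of all prohibited medications at Visit 1 (Screening/Day -14) for the duration of the study". Section 8.1.1 lists the same thing among the Visit 1 procedures ("Subjects will be instructed to discontinue the use of all prohibited medications as outlined in" Section 5.6), and SAP Section 2.2 restates it. None of the three qualifies the instruction.

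Section 5.6 lists "Anticonvulsants used for seizure disorders" and "Narcotics and narcotic containing analgesics, including tramadol", both without an exception. Other entries do carry one, for example "Antidepressants, allowed, if on a stable dose for > 30-day prior to screening period".

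The only condition attached to stopping is that consent comes first. Section 8.1.1 says consent "must be signed prior to discontinuing any prohibited medications", and footnote a to the Section 7 schedule repeats that it must be signed "prior to discontinuing any prohibited medications".

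Four provisions limit who could be affected:
- Section 5.4 requires that no prohibited drug other than rescue medication be used in screening.
- Section 5.3 #6 excludes users of drugs with a known effect on stool form, cross-referring to Section 5.6.
- Section 5.3 #7 excludes significant disease, neurologic included, that may interfere with completing the trial.
- Section 5.3 #12 excludes anyone who, in the investigator's opinion, cannot or will not meet the protocol's requirements.

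**The concern.** Read literally, the instruction tells a person whose seizures are controlled on medication to stop that medication on the day of screening. I take it as general clinical knowledge, not as something the documents state, that abrupt withdrawal of an anticonvulsant, and to a lesser degree of long-term opioids, is hazardous. A protocol that requires a list of drugs to be stopped should separate those that can be stopped for research convenience (laxatives, frequent antacids or NSAIDs) from those that treat another serious condition. For the second kind, the subject should fail screening and stay on the drug.

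What is at stake is the safety of a small number of screened people. Type I error, power and the primary analysis are not involved.

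**Working it through.** No figure in the plan bears on this point, so the check is mainly a comparison of provisions.

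**1. Is either class protected within Section 5.6?** The list has 24 entries. Eight carry some exception: antacids, enemas, laxatives/stool softeners, iron, NSAIDs, other analgesics, antipsychotics and antidepressants. Four of these are stable-dose exceptions (laxatives/stool softeners, iron, antipsychotics, antidepressants). That leaves 24 − 8 = 16 with no exception, including seizure anticonvulsants and narcotics.

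**2. Does the plan foresee current users stopping in order to enter?** Yes, in general. The consent-first rule and the Visit 1 stop instruction would have little purpose if every current user were already excluded, and the Section 5.4 criterion looks only at use during screening. These provisions do not show which drugs the authors had in mind.

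**3. Does any provision clearly remove a well-controlled seizure patient at Visit 1?**

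| Provision | Reaches this patient? | Says do not stop? |
|---|---|---|
| 5.3 #6 | Arguable: yes if the cross-reference means the whole Section 5.6 list; doubtful if limited to drugs that affect stool | No |
| 5.3 #7 | Only if controlled epilepsy counts as significant and likely to interfere with completion | No |
| 5.3 #12 | Probably, if the investigator reasons that the patient cannot do without the drug for the whole study | No |
| 5.4 | Only if the patient keeps taking the drug; one who stops as told satisfies it | No |
| 5.7 and 11.5 (removal in the subject's interest; deviation for immediate hazard) | At investigator discretion | No |

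For chronic opioids, #6 is much firmer. Section 2 of the protocol itself names opioid bowel dysfunction as a constipation-related disease, so opioids fall under #6 even on its narrow reading.

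**4. What observation follows a stop at Visit 1?** Sections 7 and 8.2.1 schedule nothing in the clinic until Visit 2 on Day 1. With no Day 0, Day −14 through Day −1 is 14 days. In that time the telephone diary covers bowel and abdominal symptoms, rescue use, and weekly IBS and constipation severity (Section 8.1.2). Visit 2 then records changes in medical history and medications, and vital signs. Under Section 9.6, adverse events are reported from Day 1, and events before the first dose go into medical history. The same section asks for serious events occurring during the study to be reported, without saying how that fits with the Day 1 start.

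**5. How many people?** Expected screened: 600 × 2 = 1,200, from the 2:1 ratio in Section 4. The number at risk is 1,200 × f, where f is the share who take such a drug and pass #6, #7 and #12. The documents do not give f. Each 0.1% would be 1,200 × 0.001 = 1.2 people.

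**The case against.** The strongest reply is that the layers work together. Section 5.4 already makes a continuing user ineligible, so the screen-fail half of the rule exists. Section 5.6 does not sort its drugs by effect on stool, so the cross-reference in #6 most naturally means the whole list. The #6 note letting stable fiber, bulk laxatives, stool softeners and probiotics continue makes most sense if other current users are out. A patient who medically needs a banned drug cannot meet the protocol's requirements and so falls under #12. Section 8.1.1 lists eligibility, history and medications before the stop instruction. For harm to occur, an investigator would have to pass over #6, #7 and #12 and also tell a seizure patient to stop treatment.

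Most of this stands, and it is why the point is narrow. What it does not supply is the other half of the rule. Section 5.4 is met by stopping, so it does not discourage stopping, and every remaining safeguard depends on interpretation or judgment.

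Four stronger readings are tempting, and the documents do not support them:
- *The consent-first rule shows that seizure or opioid patients are meant to stop.* It is a general protection, fully explained by laxatives, antacids and NSAIDs.
- *Subjects go 28 days without safety observation.* Visit 3 on Day 15, 14 + 14 = 28 days after the stop, is the first visit with a scheduled adverse event assessment. But Visit 2 is a clinical contact at 14 days, and adverse events are reportable from Day 1.
- *About 1,200 people are exposed.* That is everyone screened, not those who take either class.
- *Excluding Parkinson's disease under #5, while anti-Parkinson agents are also on the list, shows inconsistent handling of withdrawal risk.* #5 concerns central nervous system causes of constipation and was not written as a withdrawal rule.

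**Conclusion.** The point holds in a narrow form. The stop instruction is unqualified, seizure anticonvulsants are on the list with no exception or taper, and no provision clearly excludes a well-controlled seizure patient at Visit 1 or says that the drug must not be stopped to qualify. Chronic opioids are a weaker second case, because #6 probably covers them.

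The number affected cannot be estimated and is likely very small, on the assumption that most investigators would apply #6, #7 or #12 sensibly. There is no effect on the analysis. I would call this a cheap improvement: the hazard comes from following a written instruction as it stands, and removing it takes very little text.

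**What to change.** 1. Protocol Section 5.3 and the synopsis, new exclusion: *Subject requires a Section 5.6 medication that cannot be safely withdrawn (at minimum, an anticonvulsant for a seizure disorder or chronic opioid therapy).* It belongs in 5.3 because Sections 5.4 and 8.2 determine eligibility from Sections 5.2 to 5.4.
2. Protocol Sections 4 and 8.1.1, added text: *Such a subject is a screen failure and must not stop the medication for the study; the instruction to discontinue applies only to medications that can be safely withdrawn.*
3. SAP Section 2.2: align the restated sentence.

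The test should be whether the drug can be safely withdrawn. A rule excluding anyone who needs a listed drug for a medical condition could screen out ordinary laxative users, who are part of the target population. Exclusion #6 can stay as it is.

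Cost: written IRB/IEC approval of the wording (Section 11.5) across 100 to 120 sites, and a few more screen failures. No new procedure and no change to any analysis.
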